#### 4.0 OBJECTIVE(S) & HYPOTHESIS

Obstructive sleep apnea (OSA) has been estimated to affect between 2 and 4% of the U.S. population < Young T, NEJM 1993>. It is a serious, lifethreatening condition associated with obesity, hypertension, congestive heart failure, pulmonary hypertension, coronary artery disease, and cardiac arrhythmias and has an 8 year mortality rate of nearly 40% <Parrish JM, Mayo Clin Proc 2004, He J, Chest 1988>. Following general anesthesia, patients with OSA have been noted to have a significantly increased risk of respiratory complications, morbidity and mortality <Gupta RM Mayo Clin Proc 2001, Liao P, Sleep 2007, Young T, Sleep 2007, Marshall NS, Sleep 2008 >. This may be due to residual effects of inhaled anesthetics which can decrease upper pharyngeal muscle tone leading to airway compromise in OSA patients <Bell RL, Anes Clin of NA 2005>. Also, OSA patients are exquisitely sensitive to the ventilatory depressant effects of postoperative opioids, causing decreased responsiveness to hypercarbia and episodic arterial hypoxemia <Ostermeier AM, Anes Anal 1997, Stoelting, Anesthesia and Coexisting Disease 4th ed>. Currently, there is not a well-established, general anesthetic technique that will decrease the risk of complications in OSA patients. The objective of this study is to compare the postoperative recovery profile of OSA patients receiving

standard Sevoflurane inhaled anesthesia versus Sevoflurane combined with a low-dose ketamine infusion.

We hypothesize that the group of obstructive sleep apnea patients that receive low-dose intraoperative ketamine will report lower pain scores, require less supplemental intravenous Morphine, and have less frequent side effects and desaturation episodes post-operatively than the group receiving saline.

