#### 6.0 ELIGIBILITY & EXCLUSION CRITERIA

Inclusion criteria: Total of sixty-five patients, aged 19-70, scheduled to undergo laparoscopic gastric bypass surgery for morbid obesity. Patients should have a diagnosis of obstructive sleep apnea as confirmed by sleep study and are not currently using a CPAP devise. If no sleep study is available, patients should have the 4 clinical predictors of obstructive sleep apnea as described by STOP (Snoring, Tiredness during daytime, Observed apnea, high blood Pressure) screening questionnaire. <Chung, F Anesthesiology 2008>

Exclusion criteria: Patients <19 yrs, positive pregnancy test, ASA> III, history of alcohol or narcotic abuse in last 90 days, significant cardiovascular or respiratory disease (baseline oxygen saturation below 92%), significant psychiatric or neurologic disease, history of significant hepatic or renal disease (baseline creatinine>1.5), history of allergy or contraindication to anesthetic agents or ketamine including patients with increased ICP, increased IOP, severe arrhythmias, history of delirium, hallucinations, or psychosis, or history of uncontrolled seizures, or potential risk for malignant hyperthermia (family history), history of difficult intubation that would preclude standard induction of anesthesia, prisoners, persons who are mentally impaired, and non-english speakers.

Criteria for early withdrawal for the study: <2 hrs surgical time, any surgical or anesthetic complication that prevents the assessment of study variables, clinically relevant residual neuromuscular blockade or other reason for patient to require prolonged tracheal intubation following surgery.

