# 9.0 CONCOMITANT THERAPIES Not applicable

#### 10.0 DRUG INFORMATION

The risks associated with IV ketamine when used alone at doses of 1-4 mg/kg include emergence reaction. Medication package insert includes a black box warning listing: "incidence of 12%; psychological manifestations vary in severity between pleasant dream-like states, vivid imagery, hallucinations, and emergence delirium; may be assoc. w/ confusion, excitement, and irrational behavior; duration usually a few hours, recurrences up to 24h post-op in few cases; no residual psychological effects; decr. incidence in <15 y/o and >65 y/o, if IM dose, or previous exposure; decr. incidence w/ lower doses in combo w/ diazepam during

anesthesia induction and maintenance; use small hypnotic dose of shortor ultrashort-acting barbiturate to end severe emergence rxn

Other possible severe adverse reactions include: respiratory depression, laryngospasm, ICP incr., IOP incr., hypotension, severe, bradycardia, arrhythmias, delirium, hallucinations, tonic clonic movements, anaphylaxis, withdrawal syndrome (long-term use).

Other common adverse reactions include: hypersalivation, anorexia, nausea/vomiting, elevated BP, elevated HR, diplopia, nystagmus, fasciculations, depressed reflexes, hallucinations, bradycardia hypotension.

Ketamine is contraindicated or should be used with caution if patients with: hypersens. to drug/class/compon., HTN, stroke, head trauma, intracranial mass/hemorrhage, caution if ICP incr., caution if IOP incr., caution if CAD, caution if CHF, caution if thyrotoxicosis, caution if psychosis, caution if hepatic impairment, caution if acute alcoholism, caution if chronic alcohol use, caution if substance abuse, caution in elderly pts. < www.epocrates.com>

Other severe side effects are rare and are typically reversible with cessation of drug infusion. Common side effects are also typically reversible with cessation of infusion. Multiple studies have demonstrated that low-dose ketamine, when given with anesthetic induction agents and inhalational anesthetic gas, is safe and effective with few if any, adverse side effects. <Bell RF, Cochrane Review, 2005>

Investigational New Drug (IND) Application Required?: No

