# 11.0 STATISTICAL CONSIDERATIONS

Statistical analysis with *a priori* power analysis was performed to determine the number of patients per group sufficient to detect a decrease of >30% in postoperative opioid requirements on the basis of the results of Kararmaz et al., Anesthesia and Analgesia 2003. With a power of 80% and a type 1 error of 5%, it was estimated that 32 patients will be required per group. We will plan to enroll 65 patients total to account for unanticipated subject dropout. Mann-Whitney U-test will be used to compare VRS, modified Aldrete, and patient satisfaction scores. Student's t-test will be used to compare BMI, time to first analgesic, number of analgesic demands, amount of analgesic consumption and ODI. The X2 test will be used to compare frequency of side effects, race and sex distribution. The resulting values will be expressed as mean +/- SD or median and range with P< 0.05 considered statistically significant.

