#### 13.0 REPORTING ADVERSE EVENTS

Patients at risk for severe adverse reactions will be excluded from the study. This includes patients with a history of adverse reaction to ketamine, patients with increased ICP, increased IOP, arrhythmias, history of delirium, hallucinations, or psychosis, or history of uncontrolled seizures.

Patient will be removed from the study if any surgical or anesthetic complication necessitates deviation from routine anesthetic management or prevents the assessment of study variables. Also, patient will be withdrawn if clinically relevant residual neuromuscular blockade or other reason for patient to require prolonged tracheal intubation following surgery.

Any adverse events occurring in the enrolled study subjects will be immediately reported to the UAB Department of Anesthesiology Human Subjects Research Committee and the UAB IRB. As an integral element of data and patient safety monitoring, a completed departmental-level Data Protection and Patient Safety Monitoring Form will be presented to the UAB Department of Anesthesiology Human Subjects Research Committee every three months.

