# If study involves drugs or devices skip Items 19.b. and 19.c., go to Item 20, and complete the Drug or Device Review Sheet, as applicable.

- b. If hazards to an individual participant occur, describe (i) the criteria that will be used to decide whether that participant should be removed from the study; (ii) the procedure for removing such participants when necessary to protect their rights and welfare; and (iii) any special procedures, precautions, or follow-up that will be used to ensure the safety of other currently enrolled participants.

  Criteria for early withdrawal for the study: <2 hrs surgical time, any surgical or anesthetic complication that prevents the assessment of study variables, clinically relevant residual neuromuscular blockade or other reason for patient to require prolonged tracheal intubation following surgery.
- c. If hazards occur that might make the risks of participation outweigh the benefits for all participants, describe (i) the criteria that will be used to stop or end the entire study and (ii) any special procedures, precautions, or follow-up that will be used to ensure the safety of currently enrolled participants.

  The overall study will be suspended if is determined that, at any point, study procedures are not adequate to protect the participant's safety. All efforts will be made during procedures to ensure that the participant's risk is minimized.

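### Patients removed after randomization for serious complications are not kept in the side-effect comparison, which can bias it in either direction

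*Combined protocol and SAP*

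**What the plan says.** The hypothesis in section 4.0 is that ketamine patients will "have less frequent side effects and desaturation episodes post-operatively than the group receiving saline". The test is in section 11.0: "The X2 test will be used to compare frequency of side effects, race and sex distribution". That section names no analysis set. On losses it says only "We will plan to enroll 65 patients total to account for unanticipated subject dropout".

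The removal rule appears in three places:

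- **Section 13.0 (adverse event reporting).** "Patient will be removed from the study if any surgical or anesthetic complication necessitates deviation from routine anesthetic management". The same sentence adds complications that make assessment impossible, and the next withdraws patients with residual blockade or prolonged intubation.
- **Section 6.0.** Withdrawal for "any surgical or anesthetic complication that prevents the assessment of study variables, clinically relevant residual neuromuscular blockade", or another reason for prolonged intubation.
- **Human Subjects Protocol, item 19.b (the later form).** The item asks for "the criteria that will be used to decide whether that participant should be removed from the study" when hazards occur. The answer includes "any surgical or anesthetic complication that prevents the assessment of study variables" and prolonged intubation.

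Under section 8.0, patients are allocated by envelope, the syringe is handed over on the day of surgery, and study drug is given after induction and before incision. Nausea or vomiting, sedation and dysphoria are recorded in the PACU every 15 minutes.

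**The concern.** The removal triggers overlap with the outcome being compared, and they act after randomization, mostly after study drug. Section 10.0 warns: "Other possible severe adverse reactions include: respiratory depression, laryngospasm", and goes on to arrhythmias and delirium. A patient too delirious to score, or still intubated, meets a removal criterion. So may a saline patient with an opioid-related respiratory complication. Section 2.0 raises the possibility that ketamine lessens respiratory compromise, so unequal removal is a consequence the trial itself might produce. Blinding does not help, because the event itself triggers removal.

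If removed patients are left out, the comparison describes only those whose complications were mild enough, or assessable enough, to stay. A real benefit could be understated, or a harm partly hidden. Because the plan is silent, the choice could also be made after the results are known.

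**Working it through.** **1. The plan's own figures.** There are none for side-effect or removal rates. The 32 per group is sized on opioid use with no SD given, so it cannot be re-derived, and this point does not need it. The margin for losses is 65 − 2 × 32 = 1 patient. At an assumed 5% removal rate, 65 × 0.05 = 3.25 losses are expected, and P(more than one) = 1 − 0.95^65 − 65 × 0.05 × 0.95^64 = 0.84. At 2% it is 0.37. The Human Subjects Protocol raises enrollment to 150 and states no allowance.

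**2. What each rule catches.**

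- *Complication that changes anesthetic management, patient still assessable:* removed under section 13.0 only.
- *Complication that makes assessment impossible:* removed under all three.
- *Prolonged intubation:* withdrawn under all three.
- *Nausea, sedation, dysphoria or hallucination in an assessable PACU patient:* stays in.

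**3. Effect on the observed rate.** Let p be the true proportion with any side effect, s the proportion removed, and f the share of removed patients who had a counted side effect. Among patients kept, the rate is (p − s·f)/(1 − s). If f = p this equals p, so there is no distortion.

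Assume p = 0.40 in both arms, 75 per arm (150/2, equal allocation), and X2 without continuity correction at two-sided 5%. The probabilities below come from summing the binomial distributions of removals and events.

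| Removed, ketamine v saline | f | Rates seen | Significant, favoring ketamine |
|---|---|---|---|
| none | – | 40.0% v 40.0% | 2.7% |
| 5% v 5% | 1 | 36.8% v 36.8% | 2.5% |
| 3% v 1% | 1 | 38.1% v 39.4% | 3.6% |
| 5% v 2% | 1 | 36.8% v 38.8% | 4.3% |
| 5% v 2% | 0.7 | 38.4% v 39.4% | 3.3% |
| 5% v 2% | 0.4 | 40.0% v 40.0% | 2.5% |
| 10% v 2% (worst case) | 1 | 33.3% v 38.8% | about 10% |
| 10% v 2% | 0.7 | 36.7% v 39.4% | 5.2% |

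For example, (0.40 − 0.05)/0.95 = 0.368 and (0.40 − 0.02)/0.98 = 0.388.

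**4. The other direction.** Suppose ketamine truly lowers 40% to 28%. With everyone counted, power is 34% (18% at 32 per arm). If 2% of ketamine and 5% of saline patients are removed and f = 1, the rates seen are 26.5% v 36.8%, and power falls to 27% (14%). With the removal rates swapped it is inflated to 47% (24%).

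**5. A single serious reaction.** If a reaction has true rate p and a fraction g of affected patients is removed, the rate seen is p(1 − g)/(1 − p·g). With 6% v 2% and g = 0.5, this gives 0.03/0.97 = 3.1% v 0.01/0.99 = 1.0%. With g = 1 it gives 0 v 0.

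**6. Sensitivity to one patient.** In counts chosen to show this, 5/31 v 13/32 gives P = 0.031. Restoring one removed ketamine patient with an event gives 6/32 v 13/32, P = 0.055.

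**The case against.** The strongest reply is that exclusion is inferred. No sentence says that data from removed patients leave the X2 test, and the spare patient is for dropout in general. That stands. But taking patients out of the study, with no set that brings them back, makes exclusion the natural reading.

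A reader might infer that every serious side effect is left out. The documents do not support this. Removal needs a change of anesthetic management (section 13.0 only; the later form lacks that limb) or an unassessable patient. Section 8.0 lets the anesthesiologist use vasoactive drugs, fluids and fentanyl at discretion, so treated hypotension need not count as a departure. It answers untoward effects in the PACU by calling the physician, not by removal. Respiratory compromise is measured mainly by the desaturation index, which has its own t-test.

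Nor are serious events lost to oversight: section 13.0 sends adverse events to the departmental committee and the IRB at once, with a three-monthly safety form. It states no comparison by arm.

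Finally, the distortion depends on assumptions. Sections 10.0 and 12.0 expect severe effects to be rare and delirium unlikely. Intubated patients may have had none of the PACU items, so f = 1 is an upper bound. All of this limits the size of the problem, but does not make a safety comparison that depends on such events sound.

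**Conclusion.** The point holds in a limited form. Followed as written, the plan removes randomized patients for complications that ketamine may cause or prevent, then compares side effects with nothing that retains them. Some of the most serious complications, though not all, would then be missing from the comparison by arm.

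The size and direction are unknown. Under the assumptions above, modest unequal removal (3% v 1% to 5% v 2%) moves the chance of a spurious finding for ketamine from 2.7% to at most 3.6–4.3%. The reverse imbalance costs about 7 points of power (34% to 27%). Equal removal with no drug effect, or removed patients who resemble the rest, produces no distortion. The 10% v 2% row is a worst case, not an expectation. A reader might infer that the plan favors ketamine; the documents do not show that. The effect is clearest for a serious reaction counted on its own, where removal can empty the row. The wording should be changed.

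**What to change.** - **Section 11.0.** Compare side effects in all randomized patients who received study drug, by assigned arm.
- **Sections 6.0 and 13.0 and item 19.b.** Use one rule in all three. Replace removal for a complication with continued recording of PACU and 24-hour data wherever the patient can be assessed. Stopping the infusion for safety remains open.
- **Reporting.** Give the number and reason of such complications by arm. Count each as a serious event in its own row, with a risk difference and 95% CI, using exact methods if sparse. (For 4/32 v 0/32, X2 gives P = 0.039 and Fisher's test P = 0.113.)
- **Unassessable patients.** For the PACU items, repeat the comparison counting them as events and then as non-events.

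As a clarification only, one sentence could list the side-effect items and their time window.

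The cost is wording. PACU monitoring is routine and the 24-hour assessment already exists. The downsides are slightly more variability from patients whose anesthetic was changed, and a range instead of a single answer for those who cannot be scored.

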#### 12.0 PATIENT SAFETY AND DATA SECURITY MONITORING

#### Assessment of Level of Risk:

This study poses a very low level of risk to the study participants. While participating in this study, the possible risks include: experiencing side effects from low dose ketamine and possible loss of confidentiality. The most common side effect, emergence delirium is unlikely using low-dose ketamine, when given with anesthetic induction agents and inhalational anesthetic gas. Multiple studies have demonstrated safety and efficacy with few if any, adverse side effects <Bell RF, Cochrane Review, 2005>.

Oversight of this investigation will be provided by primary investigator, [name]. Additional oversight will be provided by the Department of Anesthesiology Human Subjects Research Committee and its related support staff.

The mechanisms for HIPAA compliance [including a detailed electronic personal health information (PHI) data path]:

Patient privacy will be protected through participation as per HIPPA guidelines. Patient confidentiality will be protected through password protected computers within the UAB anesthesiology department. Only study investigators listed on this IRB will have access to protected patient information.

Patients will be identified as potential study participants in the during their preoperative clinic visit. Study coordinator will be contacted to provide the patient written and verbal informed consent several days prior to surgery.

Study coordinator will provide the patient written and verbal informed consent several days prior to surgery. Patient will be required to return home to read informed consent along with study background and protocol information. They will contact study coordinator if interested in participating in the study.

#### 13.0 REPORTING ADVERSE EVENTS

Patients at risk for severe adverse reactions will be excluded from the study. This includes patients with a history of adverse reaction to ketamine, patients with increased ICP, increased IOP, arrhythmias, history of delirium, hallucinations, or psychosis, or history of uncontrolled seizures.

Patient will be removed from the study if any surgical or anesthetic complication necessitates deviation from routine anesthetic management or prevents the assessment of study variables. Also, patient will be withdrawn if clinically relevant residual neuromuscular blockade or other reason for patient to require prolonged tracheal intubation following surgery.

Any adverse events occurring in the enrolled study subjects will be immediately reported to the UAB Department of Anesthesiology Human Subjects Research Committee and the UAB IRB. As an integral element of data and patient safety monitoring, a completed departmental-level Data Protection and Patient Safety Monitoring Form will be presented to the UAB Department of Anesthesiology Human Subjects Research Committee every three months.

g. Describe the process that ensures that all persons assisting with the research are adequately informed about the protocol and their research-related duties and functions: At study initiation, meetings will be held with all study personnel to discuss the specifics of the project and to address any questions raised. All personnel involved in obtaining informed consent will be current in their training in the protection of human subjects involved in research. All personnel and Anesthesia Providers will be given a copy of a study summary and/or outline for guidance. 4. Funding Is this study funded? □Yes ⊠No If No, specify that costs of the study will be covered by funds from the UAB department or other source named: Department of Anesthesiology & Perioperative Medicine If Yes, attach one copy of completed application or request for funding sent to sponsor, and complete a-d. a. Title of Grant or Contract: **b.** PI of Grant or Contract: **c.** Office of Sponsored Programs Proposal Number: (or enter "Pending" and provide upon receipt from OSP) **d.** Sponsor, Funding Route (check and describe all that apply): ☐ Gov't Agency or Agencies—Agency name(s): □ Department of Defense (DoD): Identify DoD component:\_\_\_\_ □ Department of Energy (DOE) ☐ Department of Justice (DOJ) ☐ Department of Education □ NIH Coop. Group Trial—Group name: ☐ Private Nonprofit (e.g., Foundation)—Name: □ Industry, investigator-initiated—Name:\_\_\_\_ Describe the funding arrangement: Note. Western IRB reviews industry-sponsored protocols unless the investigator initiated the research, or the study qualifies for expedited review or involves gene therapy. ☐ UAB Departmental/Division Funds—Specify: 5. Locations Involved a. Describe the facilities available for the conduct of the research. For research on UAB campus, include building names and room numbers: b. Indicate all "performance sites" that will provide space, services, facilities, potential or actual participants, or other support for this protocol. □ The Kirklin Clinic (TKC) ☑ University of Alabama Hospital (UAHosp) ☐ The Children's Hospital of Alabama (TCHA) □ Callahan Eye Foundation Hospital (CEFH) □ UAB Highlands ☐ Jefferson County Dept. of Health (JCDH) ☐ Birmingham Veterans Affairs Medical Center (BVAMC) ☐ General Clinical Research Center (GCRC)—inpatient

	
 
General Clinical Research Center (GCRC)—outpatient
 
General Clinical Research Center (GCRC) at The Kirklin Clinic (TKC)
 
Other (i.e., Any performance site not listed above, including those covered by subcontracts related to this protocol)—Describe:
 

	c. Is this study a clinical trial requiring clinical services at one of the performance sites listed in Item b above? □Yes ⋈N If Yes, Fiscal Approval Process (FAP)-designated units complete a FAP submission and send to [contact]. For more on the UAB FAP, see www.uab.edu/osp/clinical-billing-review.
	d. Is this a field study?  ☐Yes ☑N  If Yes, describe the community and include information about how the communit will be involved in the design, implementation and analysis of the research. This would include focus groups, training local facilitators/community health advisors:
	e. Is the study to be undertaken within a school, business, or other institution that does not have an institutional review board? □Yes ☒N  If Yes, attach a statement of any contacts with and approvals from the appropriate institution officials.  Note. Documentation of all such approvals must be received by the UAB OIRB before IRB approval will be issued.
	f. Has this protocol or project been reviewed by another IRB, similar review board, of departmental review committee(s) that authorizes the use of its patient populations? □Yes ⋈N If Yes, provide name of the review board(s): and for each board listed enter either the date of latest approval(s) or "PENDING": or reasons not approved: If this protocol is subsequently rejected or disapproved by another review board, the UAB IRB must be notified promptly. Attach copies of approvals/disapprovals.
	g. Will any of the participants be from the Birmingham Veterans Affairs Medical Center? □Yes ☑N If Yes, attach VA IRB approval or notification from the VA Research and Development Department that the study has been submitted to the VA IRB for review.
	h. Will the study be conducted at or recruit participants from the Jefferson County Department of Public Health (JCDH)? □Yes ☒N If Yes, attach notification that the protocol has been approved by JCDH or the Alabama Department of Public Health IRB.
6	. Multi-Site Studies
	
 
a. Is the investigator the lead investigator of a multi-site study?
 
b. Is UAB a coordinating site in a multi-site study?
 
c. If you answered Yes to a or b, describe the management of information obtained in multi-site research that might be relevant to the protection of participants. Include, at a minimum, the following items: 
 
○ IRB approvals from other sites
 
 
 

				Interim results. Protocol modifications.		
7.		_		Vill any drugs or supplements be used/studied in this protocol ttach the Drug Review Sheet.	?	⊠Yes □No
8.	ot	her	thar	Will any devices be studied in this protocol or used for a purp n for which they were approved by the FDA? ttach the Device Review Sheet .	ose	□Yes □No
9.		Do	es th	Approvals his project involve the use of radioisotopes? , attach documentation of approval from the Radiation Safety	/ Divi	□Yes ⊠No sion.
	b.	me If	easle Yes ,	his project include patients with contagious infections (e.g., nes, chickenpox, TB, meningitis)?		□Yes ⊠No
	C.	De If	part Yes , e ma	his project involve obtaining remnant biopsy or surgical mater tment of Pathology or any other source? s, attach documentation of approval from the entity or individuaterials (e.g., the UAB Division of Anatomic Pathology Released als ).	ual pr	□Yes ⊠No oviding
	d.	boo oth If the	dy fl ner s Yes , e ma	his project require obtaining any remnant clinical laboratory s luids, or microbiological isolates from the Department of Path source? s, attach documentation of approval from the entity or individuaterials (e.g., the UAB Division of Laboratory Medicine Releaserals ).	ology ual pr	or any □Yes ⊠No oviding
	e.	If	Yes,	his project use stored (existing) specimens from a repository?  a, attach documentation of approval for use of specimens, and ag specimens are labeled:		□Yes ⊠No cribe how
10	Do fu	oes ture Ye s	this e res s , co	Specimens project involve collecting specimens from participants and store search? omplete a-h. If no, skip to Item 11 w will specimens be obtained, processed, distributed, and store		them for □Yes ⊠No
		b.		w will specimens be labeled (e.g., unique identifier, medical recial Security number, name, date of birth)?	cord	number,
		c.	How	w will clinical data associated with the specimens be collected	and s	stored?

 Unanticipated problems involving risks to participants or others. (For example, if there is an unanticipated problem involving risks to participants or others, which site is responsible for reporting it?)

	specimens?	
e.	What steps will be taken to maximize the confidentiality of linked ide For example, procedures could include using a password-protected contact database to link identifiers, with limited personnel knowledgeable of password, or coded identifiers released without the ability to link to contact a link in the confidential contact and the confidential contact and the confidential contact and	omputer the
f.	Will specimens be shared with other investigators in the future?  If Yes, what identifiers, clinical information and demographic information be shared; or will the specimens be stripped of identifiers (i.e., anony Also if yes, outline your procedure for assuring IRB approval for release prior to release of specimens.	/mized)?
	Note. Investigators who receive and/or use these specimens must de approval from the appropriate IRB(s) before the specimens may be in	
g.	Will biological samples be stored for future use?  If Yes, indicate whether they will be used for the disease under study protocol or research on other diseases.	□Yes ⊠No y in this
h.	Is genetic testing planned?  If Yes, describe the planned testing here and see "DNA/Genetic Test Guidebook for consent requirements.	□Yes ⊠No ing" in the
Does huma  If Ye vaccin Recor	this project involve gene therapy or administering recombinant materins?  s, submit the Gene Therapy Project Review Panel Report –OR- If this in the trial that is exempt from the NIH Guidelines For Research Involving mbinant DNA Molecules, submit the Protocol Oversight Review Form Form Trials .	□Yes ⊠No s a
Will the health medic past,	PAA Privacy and Security he PI or others obtain, review, or make other use of participants' "person information" (i.e., information, whether oral or recorded in any formoum that (a) is created or received by a health care provider and (b) relepresent, or future physical or mental health or condition of an individuation of health care; or payment for provision of heath care)?	or ates to
If Ye a. Wi	s , complete a-e as described. Il the data/information be stored or managed electronically (on a comp	uter)? ⊠Yes □No

d. What participant-identifying information will be collected and linked to the

11.

12.

D.	authorization from another institution or entity (e.g., insurance company, collaborating institution).  If Yes, attach copy of privacy notices from institution/entity, and provide the name of institution/entity:
c.	Indicate which, if any, of the listed entities below would provide information or maintain health information collected for this protocol and/or where health information that been collected will be stored/maintained.  ☑ The Kirklin Clinic  ☑ University of Alabama Hospital  ☐ The Children's Hospital of Alabama  ☐ Callahan Eye Foundation Hospital  ☑ UAB Highlands  ☐ Jefferson County Department of Health  ☐ School of Dentistry  ☐ School of Medicine  ☐ School of Medicine  ☐ School of Optometry  ☐ University of Alabama Health Services Foundation  ☐ UAB Health Centers  ☐ Viva Health  ☐ Ophthalmology Services Foundation  ☐ Valley Foundation  ☐ Medical West - UAB Health System Affiliate  Health System Information Systems:  ☐ HealthQuest  ☑ Cerner Millennium (Lab, Radiology, UED, Surgery)  ☐ EMMI - Master Member Index  ☑ Horizon - IPV (IVR/CDA/CRIS)  ☐ CareFlow Net  ☐ Eclipsys (PIN)  ☑ IMPACT
	□ None—If None, skip to Item 13.
d.	Indicate which of the listed identifiers would be associated/linked with the protected health information (PHI) used for this protocol.  Names Geographic subdivisions smaller than a State Elements of dates (except year) related to an individual Telephone numbers Fax numbers Email addresses Social security numbers Medical record numbers Health plan beneficiary numbers Account numbers Certificate/license numbers

	United actioners and serial numbers
	☐ Device identifiers and serial numbers
	☐ Biometric identifiers
	☐ Web universal resource locators (URLs)
	□ Internet protocol address numbers
	☐ Full-face photographic images
	☐ Any other unique identifying number—Describe:
	Note. Codes are not identifying as long as the researcher cannot link the data to an individual
	□ None—If None, skip to Item 13.
e.	Choose one plan to describe your use of the personal health information: 
 
The data collected meet the specifications for a "limited data set"
 
Attach Data Use Agreement or Business Associate Agreement
 

	Research staff will obtain authorization from each patient to use the information —Attach Patient Authorization form, complete except for patient name and IRB protocol number
	
 
PI requests Waiver of Patient Authorization to use the information
 
Attach Waiver of Authorization and Informed Consent form
 

